### 12.3 CAREER DEVELOPMENT PLAN

The supplemental funding mechanism included a career development and mentoring plan, centered around holistic growth as a future physician scientist. The primary goals for [name] career development plan include (1) learning to independently lead and coordinate a scientific research project; (2) communicate and manage a large research team; and (3) produce high-quality research manuscripts and presentations of findings on national platforms.

The research timeline, presented below, includes the primary goals of improving scientific research knowledge and production of manuscripts and long-term goals of ultimately completing a K08 grant application by 2024.

### Research Timeline

Year	Year 1	Year 2	Year 3	Year 4
Skills	Data management and methods skill building	Quantitative/Qualitative analysis methods	Manuscript production	Presentations and future funding
Aims	DEI supplemental qualitative and quantitative methods and manuscript production  Preparation for data analysis to start at completion of parent study	Aim 1: Initiate semi-structured interviews  Aim 2: Complete data collection and analysis	Complete manuscript of supplemental data  Apply for additional funding with preliminary data	Complete manuscript assistance for parent data grant  Submit K08 with supplemental data
Mentorship	[name]			

## 13 APPENDIX C: RESEARCH SUPPLEMENT – INVESTIGATING THE BARRIERS TO IMPLEMENTATION AND THE APPROPRIATENESS OF VR CONTENT ACROSS DIVERSE CULTURES: A RETROSPECTIVE MIXED METHODS STUDY

### 13.1 BACKGROUND AND APPROACH

Digital therapeutics such as virtual reality (VR) technologies have the potential to expand our approach to chronic pain management. While this novel modality continues to be investigated, there are discrepancies across individuals of differing sociodemographic backgrounds in their engagement and use of VR. A recent study published in the *Journal of Racial and Ethnic Health Disparities* found that Black and Hispanic patients were up to five times less likely to have access to digital health information. Another recently published article in *The Lancet* stressed the need for designing digital health applications to meet the needs of women – especially with racial or ethnic minority backgrounds. Other studies reported similar differential uptake, interaction, and use of virtual reality based on geography and age. Beyond general digital medicine, virtual reality as an end consumer product has been found to be subject to similar disparities in uptake and use across multiple sociodemographic factors.

Understanding barriers to uptake of novel therapeutic technologies is essential for formulating solutions that can establish equity and inclusiveness when deploying VR in healthcare to a diverse population. Failure to address these sociodemographic disparities can result in disadvantaged groups being unable to optimally utilize alternative non-opioid digital treatments and thus may require more traditional treatments including opioids. To achieve equity, we must verify that the digital therapeutic content is appropriate and accessible across diverse cultures—an investigation that is instrumentally important for the development of future VR applications. To that end, in this supplemental, mixed methods study we seek to correlate PRO data collected in the parent study with newly collected and subsequently quantized qualitative data acquired from individual participant interviews.

#### Approach

An NIH commissioned report on a “best practices” approach of mixed methods research (MMR) described MMR as “focusing on research questions that call for real-life contextual understandings, multi-level perspectives, and cultural influences...It is a systematic and rigorous form of inquiry that uses

methods of data collection such as in-depth interviews, ethnographic observation, and review of documents."

In this supplemental study, we will conduct MMR employing NIH best practice methodology to better understand the barriers to VR implementation and the appropriateness of VR content across diverse cultures. This process will follow an embedded mixed methods design (QUAL(quan)) in which we will sample up to 35 individuals who have completed their participation in the skills-based VR therapy treatment arm of either the parent study (STUDY00000631) or another concurrently running study that employs the same intervention in its treatment arm (STUDY00001262). We plan to sample from this additional source (STUDY00001262) to ensure the maximal sampling of the targeted subgroups as identified by this supplement.

Potential subjects will be identified and considered eligible for participation in this study based on their current timepoint of participation within the respective study they are currently enrolled in (STUDY00001262 or STUDY00000631). For the parent study (STUDY00000631), this is defined as any participant in the active treatment arm that has completed their day 60 PROMIS Pain Interference survey. For the concurrently running study (STUDY00001262), this is defined as any participant in the active treatment arm that has completed their week 8 PROMIS Pain Interference survey. The rationale for these criteria is the time-equivalency of data points, as this measure shall be used in further analyses within this supplemental study. The other criterion for eligibility is that the individual is 18 years or older. All participants that meet these criteria will be considered for participation in this sub-study.

All identified potential participants will be contacted via phone calls (see phone script in local files). Within this call, subjects will be informed on the goals and methods of this study and their anonymity and compensation should they agree to participate. Finally, they will be informed on the possibility of being assigned to an AI-powered interviewer and the data protection measures that have been emplaced for such a modality. At the end of the call, verbal consent will be obtained from the participant and said consent will be documented within research notes. An interview time and date will be scheduled with the participant and a follow-up confirmation email will be sent to them directly after the call that has the information sheet for this study attached. Two days before their scheduled interview, participants will be sent a reminder email that restates the date and time of their interview and includes the link to the Zoom call on which the interview will be held.

These individuals will subsequently be randomized into two groups to participate in a one-on-one (1:1) semi-structured interview exploring their beliefs and experiences of the VR intervention during their time in the parent study. Considering the subject and focus of this interview, no PHI is intended to be asked of the participants nor recorded for the purposes of this study. The first group will have standard 1:1 semi-structured interviews led by a trained social scientist. Participants in the second group will also have 1:1 semi-structured interviews, but these interviews will be led by an artificial intelligence (AI)-powered virtual social scientist. This AI interviewer is a version of GPT4 that has been iteratively refined by the study team to follow best practices in conducting 1:1 semi-structured interviews through prompt parameters. The refined prompt parameters and set interview questions will be automatically given to GPT-4 upon each initialization of the GPT4-powered AI interviewer. These prompt parameters and interview guide are set or "locked", as it is not intended for the purposes of this investigation to implement revisions or improvements of the AI interviewer based on the data received during any of the interviews. Regarding collected data, all information collected during the interview (e.g., interview transcripts) and all data uploads/downloads between the interview software and GPT4 will be encrypted, transmitted, and stored in Microsoft Azure services with whom we have an executed business agreement that all data storage will meet or exceed HIPAA requirements.

Transcripts created by this process will be coded and analyzed independently by both AI and human social scientists. This analysis will follow a general, open-coding approach wherein first level codes will be created inductively from the data with refined second-level codes created from the first level. Results yielded from these analyses will be compared qualitatively to assess the thematic coverage, breadth and overlap between the results generated by the AI and human social scientists.

A later analysis will use only the second-level codes generated by the human social scientists. The human-generated second-level codes will be quantized by calculating their frequencies of occurrence in each transcript. These code frequencies will be used to identify qualitative factors that may be correlated with the participants' PRO data from the parent study. Additionally, we will compare how these significant factors and the overarching qualitative themes differ across the demographic groups of interest. Successful completion of this supplemental study will guide future VR development and research to be more inclusive of and sensitive to diverse racial/ethnic, socioeconomic, geographic, gender, and age populations. Finally, we will evaluate the feasibility of using an AI-powered virtual social scientist to both collect and analyze qualitative data.

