### 6.3 MEASURES TO MINIMIZE BIAS: RANDOMIZATION AND BLINDING

We will allocate study participants using a random number generator to assign blocks of 3, 6, 9, or 12 to ensure there is an equal distribution in the EaseVRx skills-based group vs. the EaseVRx-Distraction group vs. the EaseVRx-Sham group. Participants, their clinical providers, and study statisticians will be blinded to the study arm. The groups will be labeled as A, B or C at random. A clinical research coordinator will ship the headset containing the assigned program to the participant and enter the group label into the log of enrolled participants. Datasets will be provided to the statistician using these group labels. The research coordinator who maintains the list of randomization assignments will not call participants on the telephone. Because the intervention is conducted in participants' homes and the data are collected remotely, the participants will not encounter each other and thus will be less likely to guess their study arm assignment. We anticipate there will be no circumstances during the study that require unblinding of an individual participant or a whole group because we do not expect any related SAEs to occur with this low risk intervention.

We have restructured the block randomization module within REDCap with stratification based on the 4 sites of recruitment (1 – pain clinic, 2 spine clinic, 3 – rheumatology clinic, 4 – Deep6). Randomization will be performed on a 1:1:1 basis across the 3 treatment groups and stratified across the 4 treatment sites with random block sizes (3, 6, 9, or 12). Allocation tables will be generated using STATA v16 software and uploaded into REDcap for patient allocation.

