## 13.2 AIMS AND METHODOLOGY

### **Aim 1: Understand any barriers to implementing therapeutic VR technologies across diverse populations and learn how cultural differences influence perception of the VR content.**

[figure not shown]
To achieve this aim, we will interview a subset of participants by employing purposive sampling; participants who were enrolled in the skills-based VR arm of the parent study will be chosen based on criteria to maximize diversity across race/ethnicity, socioeconomic brackets, geography (based on zip-code: rural and non-rural), gender, and age. Interviews will be performed via Zoom video conferencing platform, and only the audio (not video) of the interviews will be captured. Interviews will be semi-structured to accommodate open, constructive dialogue. Prior to the first interview, we will develop a guide for interviewers that includes participant instructions, open-ended questions, and scripted probes to expand on themes. Interview questions will be tailored to target what barriers interviewees experienced while using VR and how they perceived the VR content in terms of their own cultural framework. Each interview is expected to last no more than 60 minutes. The audio recordings will be transcribed for subsequent analyses. Each subgroup will attempt to include at least five participants; to accommodate this diversity, at least 30 subjects will be recruited. Recruitment will continue until 1) at least 30 subjects have been interviewed and 2) thematic saturation has been established as defined by 3 consecutive interviews with no new emergent themes.

Upon completion of the interviews, trained social scientists will perform a general qualitative analysis via the open coding of the transcripts using ATLAS.ti software, including coding of participant language and classification of vocabulary into major and minor concepts. The evaluation process will generate recurring key words, phrases, and quotes, which can further be divided and compared among the subgroups. All participants will be assigned to five subgroups: race/ethnicity, socioeconomic bracket, geography, gender, and age. For each of these subgroups, we will use ATLAS.ti to generate code count histograms within major and minor concepts and will develop a network to depict a framework describing the breadth and depth of concepts. The result will identify differences among the subgroups and provide feedback for developing future, more inclusive VR content.

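### Appendix C contradicts itself on timing, and its working rule allows Skills-arm-only contact and interviews before the Day 90 self-reports

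*Protocol*

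**What the plan says.** Protocol section 13.1 (Approach) describes the sub-study sample as up to 35 "individuals who have completed their participation in the skills-based VR therapy treatment arm", drawn from this trial or from a concurrent study of the same intervention. The next paragraph judges eligibility "based on their current timepoint of participation within the respective study they are currently enrolled in". For this trial it defines the eligible person as "any participant in the active treatment arm that has completed their day 60 PROMIS Pain Interference survey". The reason given for Day 60 is that it matches the week 8 score of the other study in time.

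This trial has two immersive arms, so the phrase for the active arm is loose. The sampling sentence and section 13.2 Aim 1 show that the Skills-Based arm is meant: "participants who were enrolled in the skills-based VR arm of the parent study will be chosen based on criteria to maximize diversity".

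Those selected are telephoned. On that call "subjects will be informed on the goals and methods of this study", and an information sheet follows by email. They then have a "semi-structured interview exploring their beliefs and experiences of the VR intervention during their time in the parent study", of at most 60 minutes (section 13.2).

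Section 6.3 commits the trial to blinding: "Participants, their clinical providers, and study statisticians will be blinded to the study arm". It also keeps the coordinator who holds the assignment list from telephoning participants. Section 4.4 defines completion by the Day 90 survey.

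**The concern.** Completing participation and completing the Day 60 survey are different events, and only the second is written as an eligibility rule. Someone who meets it may still owe the Day 75 and Day 90 surveys. Nothing in Appendix C delays the call or the interview until those are in, and the appendix does not mention the parent trial's blinding.

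Two mechanisms follow. First, a long conversation about the program is attention that the Distraction and Sham arms do not get. That holds even if the arm is never named. Second, the call list is itself defined by allocation, so explaining why the person was chosen could let them infer their arm.

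Either mechanism would act on self-reports from one arm. The comparisons exposed are Skills versus Sham and Skills versus Distraction at Day 90. The perceived-arm question, also asked at Day 90 and listed as a subgroup variable in section 9.4.7, could be affected too.

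**Working it through.** **Timing**

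| Place | What it sets |
|---|---|
| Section 13.1, sampling sentence | Participation completed |
| Section 4.4 | Completion = Day 90 survey |
| Section 13.1, eligibility rule | Day 60 PROMIS-PI survey completed, still enrolled |
| Section 1.3 | Day 90 visit has a +6-day window |

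Gap between the eligibility rule and completion: 90 − 60 = 30 days. If the Day 90 survey comes at the end of its window: 96 − 60 = 36 days.

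**What falls in the gap**

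- Exposed: the Day 75 pain-interference survey, and at Day 90 pain interference, sleep, anxiety, PCS SF-6, PGIC and perceived arm. Sections 9.4.3 (protocol) and 4.6.2 (SAP) present the secondary MMRM p-values for Day 90 only.
- Not exposed: the Day 30 primary endpoint, and Day 60 pain interference, which is already submitted when the rule is met.
- Not directly exposed to self-report bias: MME, which section 8.1 takes from the EHR, possibly supplemented by CURES.

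**How many Skills participants**

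Inputs: randomization planned to end 5 September 2023 (section 8.1); Appendix C added 12 September 2023 (section 14); version 8.1 dated 19 October 2023; 10 randomized per month (section 5.5); 1:1:1 allocation (section 6.3). Day counting is assumed to start at randomization.

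Count = (days of randomization not yet at Day 90) ÷ 30.44 × 10 ÷ 3.

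- At 12 September 2023: randomized 15 June to 5 September = 83 days. 83 ÷ 30.44 × 10 = 27.3 in all; ÷ 3 = 9.1 in Skills (9.7 if Day 96 is used).
- At 19 October 2023: randomized 22 July to 5 September = 46 days. 46 ÷ 30.44 × 10 = 15.1 in all; ÷ 3 = 5.0 in Skills (5.7 if Day 96 is used).

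On these dates the last participant reaches Day 60 on 4 November 2023 and Day 90 on 4 December 2023.

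**How large a shift**

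The documents give no figure for the effect of such contact. Assume each contacted person's Day 90 T-score moves by d points, with d from 2 to 5 shown. Shift in the Skills mean = (number contacted ÷ 120) × d, with 120 per arm from SAP section 3.3.

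For scale, protocol section 9.2 uses a change-score SD of √(10² + 10²) = 14.14. With 120 per arm and 0.025 per comparison, a simulation with this SD gives 83.6% power against the plan's 83%, so these are the plan's own inputs. SE of the arm difference = 14.14 × √(2/120) = 1.83.

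| Contacted | d = 2 | d = 3 | d = 5 |
|---|---|---|---|
| 5 | 0.08 (0.05 SE) | 0.13 (0.07 SE) | 0.21 (0.11 SE) |
| 9 | 0.15 (0.08 SE) | 0.23 (0.12 SE) | 0.38 (0.21 SE) |

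If the SD were 10 rather than 14.14, the SE would be 10 × √(2/120) = 1.29, and 9 people at d = 3 would give 0.23 ÷ 1.29 = 0.18 SE.

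**The case against.** The best defence is that the sub-study is meant for people who have finished. The appendix title calls it retrospective, the sampling sentence says participation is complete, Aim 1 uses the past tense, and section 13.3 contrasts withdrawn participants with completers. Day 60 may be only a floor to make sure the score needed for the correlation exists. This is a plausible account of intent, but it does not remove the eligibility rule or its reference to current enrollment, and no sentence bars earlier contact. What stands is that early contact is permitted, not that it is the declared plan.

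Three stronger readings are tempting, and the documents do not support them.

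- A reader might infer that Skills participants are told their arm. No passage says so. The phone script is held in local files and, like the information sheet, is not in the documents. Goals and methods can be explained without naming an arm.
- A reader might infer that every secondary endpoint is compromised. Day 60 pain interference and MME are outside the self-report mechanism, as set out above.
- A reader might take the 35 interviewees as 35 ÷ 120 = 29% of the arm. Some may come from the other study, all earlier Skills completers are eligible, and the planned dates leave only about 5 to 9 people before Day 90.

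Even 9 is generous in one respect: it assumes that each person is an adult, is chosen under purposive sampling, agrees, and is reached in time.

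**Conclusion.** The contradiction in section 13.1 is real and should be corrected. As written, the working rule permits one-arm contact before the self-reported Day 90 secondary endpoints, PGIC and the perceived-arm question. Unblinding is possible but not shown. The primary conclusion of the trial is not touched.

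The likely effect is small: 0.08 to 0.23 points on the Skills mean for 5 to 9 people and an assumed shift of 2 to 3 points, or roughly 0.05 to 0.12 of the standard error of an arm difference. It would nevertheless be systematic, in one arm, and avoidable.

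The count rests on planned accrual and dates; the actual number is unknown and could be higher or lower. If day counting starts at onboarding rather than randomization, more people would be in the gap. Each 30 days of lag adds about 30 ÷ 30.44 × 10 ÷ 3 = 3.3 Skills participants.

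**What to change.** Reconcile the two sentences in section 13.1 so that no participant of this trial is called or interviewed for Appendix C until the Day 90 survey, including the perceived-arm question, is completed or its window (Day 90 + 6 days) has closed. Tying the rule to the window as well as the survey matters: requiring a completed Day 90 survey would shut out people who miss it and the withdrawn participants whom section 13.3 allows as a fallback.

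Keep the Day 60 PROMIS-PI score as the data point for the correlation. The time-matching rationale concerns which score is used, not when the person is interviewed.

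Report how many participants were contacted before Day 90, by date and type of contact, and add a sensitivity analysis of the Day 90 endpoints for them. One option is to refit the models with their post-contact scores set to missing.

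The cost is a short text change, one supplementary analysis, and interviews that start up to about 36 days later.

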## 13.2 AIMS AND METHODOLOGY

### **Aim 1: Understand any barriers to implementing therapeutic VR technologies across diverse populations and learn how cultural differences influence perception of the VR content.**

[figure not shown]
To achieve this aim, we will interview a subset of participants by employing purposive sampling; participants who were enrolled in the skills-based VR arm of the parent study will be chosen based on criteria to maximize diversity across race/ethnicity, socioeconomic brackets, geography (based on zip-code: rural and non-rural), gender, and age. Interviews will be performed via Zoom video conferencing platform, and only the audio (not video) of the interviews will be captured. Interviews will be semi-structured to accommodate open, constructive dialogue. Prior to the first interview, we will develop a guide for interviewers that includes participant instructions, open-ended questions, and scripted probes to expand on themes. Interview questions will be tailored to target what barriers interviewees experienced while using VR and how they perceived the VR content in terms of their own cultural framework. Each interview is expected to last no more than 60 minutes. The audio recordings will be transcribed for subsequent analyses. Each subgroup will attempt to include at least five participants; to accommodate this diversity, at least 30 subjects will be recruited. Recruitment will continue until 1) at least 30 subjects have been interviewed and 2) thematic saturation has been established as defined by 3 consecutive interviews with no new emergent themes.

Upon completion of the interviews, trained social scientists will perform a general qualitative analysis via the open coding of the transcripts using ATLAS.ti software, including coding of participant language and classification of vocabulary into major and minor concepts. The evaluation process will generate recurring key words, phrases, and quotes, which can further be divided and compared among the subgroups. All participants will be assigned to five subgroups: race/ethnicity, socioeconomic bracket, geography, gender, and age. For each of these subgroups, we will use ATLAS.ti to generate code count histograms within major and minor concepts and will develop a network to depict a framework describing the breadth and depth of concepts. The result will identify differences among the subgroups and provide feedback for developing future, more inclusive VR content.

